Virus-infected cells secrete a broad range of IFNs which confer resistance to yet uninfected cells by triggering the synthesis of antiviral factors. The relative contributions of the various IFN subtypes to innate immunity against viral pathogens that infect the respiratory and gastrointestinal tract was determined using mice lacking functional receptors for type I IFN, type III IFN, or both. Results found that Lambda plays an important role in the defense against several human pathogens that infect the respiratory tract, such as influenza A virus, influenza B virus, respiratory syncytial virus, human metapneumovirus, and SARS-CoV [12]. These viruses were more pathogenic and replicated to higher titers in the lungs of mice lacking both IFN receptors than in mice with single IFN receptor defects. Interestingly, SARS-CoV was present in feces from infected mice lacking receptors for both type I and type III IFN but not in those from mice lacking single receptors, supporting the view that Lambda contributes to the control of viral infections in epithelial cells of both respiratory and gastrointestinal tracts (Mordstein et al 2010). Based on this preliminary data, the WHO has recently included peginterferon lambda in its landscape analysis of potential therapeutics for COVID-19 [13].

5 Study Design

This is a Phase 2b, single-center, randomized, single-blind, dummy-placebo controlled study to evaluate the efficacy and safety of one dose of peginterferon-lambda-1a administered by injection (Lambda) for the prevention of COVID-19 in persons with high-risk exposure.

This study will enroll 164 participants with household high risk exposure to an individual with laboratory confirmed COVID 19 infection who will be followed using the PROTECT protocol for a duration of 4 weeks. Males and females aged greater than 18 years will be randomized in a 1:1 ratio to active: placebo arms and evaluated in two groups based on RT-PCR testing for SARS-CoV-2 infection at study entry.

Group A Prevention cohort: Non-hospitalized household contacts of individuals with confirmed COVID -19 infection who test RT-PCR negative for SARS-CoV-2 at study entry

Group B Treatment cohort: Non-hospitalized household contacts of individuals with confirmed COVID-19 infection who test RT-PCR positive for SARS-CoV-2 at study entry.

Enrollment will occur in two Steps.

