13.1 Sample Size and Power Considerations

The planned sample size for the trial is 164 participants enrolled and randomized in a 1:1 ratio to lambda interferon-1a versus placebo injection. This sample size is based on the expectation that approximately 32.5% of participants who are enrolled have evidence of SARS-CoV-2 at study entry (an intermediate value consistent with the 25 – 40% infection range that we expect for the study outcome in the placebo group), thus around 110 will be will have no evidence of SARS-CoV-2 infection (Prevention Cohort) at enrollment and around 54 participants will have evidence of SARS-CoV-2 infection (Treatment Cohort). The Treatment Cohort represents an exploratory pilot study to provide estimates of antiviral efficacy for early COVID-19. Power estimates for the study are based on the Prevention Cohort and incorporate the following assumptions (multiple credible scenarios are presented):

The primary analysis for the efficacy/prevention of infection with SARS-CoV-2 in the Lambda interferon-1a and the placebo groups using proportional odds model and a two-sided Type I error rate (α) of 0.05. Since participants in both the Prevention and Treatment Cohorts will be dosed after entry, we anticipate that few, if any participants will not start treatment and be excluded from the primary analysis. Further, given the nature of COVID-19, we anticipate low rates of loss to follow-up before the primary endpoint (Day 14). We expect the incidence of new COVID-19 in the placebo group to be between 25% to 40%, thus we will perform calculation for these edge-case scenarios. In addition, we will be offering enrollment to all adults in a household (~2 per household), our analysis sample will be clustered-correlated by household. However, there is no preliminary or published data to model within-cluster correlation. Thus we are modeling scenarios where the effective sample size is as high as 110 individuals, or as low as the number of households of 55. In all scenarios, we are expecting that the cumulative infection fraction for the lambda interferon will be 5%.

Cumulative Infection Percentage in Placebo	Effective sample size	
	N= 110 individuals	N = 55 family clusters
25%	80.1%	36.1%
40%	99.6%	84.0%

We note that we have 80% or greater power (and Type II error rate beta of 0.2 or smaller) in a large range of scenarios.

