13.2 Statistical Analysis

13.2.1 Analyses will include all randomized participants Our primary analysis for both the prevention and treatment cohorts (outcomes of non-infection and resolution, respectively) will be mixed model logistic regression correcting for within-household correlation as a random effect. In addition to the placebo cumulative infectivity and odds ratios, we will express the overall

cumulative incidence of infection and the difference between lambda interferon vs. placebo using nonlinear combination (i.e., inverse logit of the placebo and active treatment groups and the difference of these after the inverse logit transformation). Statistical inference will use a two-sided Type 1 error rate of 0.05 and 95% confidence intervals.

For the exploratory treatment cohort, we will similarly examine clearance of infection.

In addition, we will perform survival analysis for time to infection in the prevention cohort and time to infection clearance in the treatment cohort, modeling within cluster correlation of hazard as a random effect (frailty).

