13.2.2 Analysis of Secondary outcomes including adverse events

For secondary time to event outcomes, we will perform survival analysis for time to infection in the prevention cohort and time to infection clearance in the treatment cohort, modeling within cluster correlation of hazard as a random effect (frailty).

Analysis of AE data will primarily be descriptive based on MedDRA coding of events. The proportion of participants experiencing an SAE and the proportion experiencing a Grade 3 or higher. AE will be compared between randomized arms using Fisher's Exact Test. Statistical analyses for the InFLUenza Patient-Reported Outcome (FLU-PRO[®]) measure of ordinal data of independent groups with more than three samples will utilize the Kruskal-Wallis H method.

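### Section 13.2.2 gives serious and Grade 3 or higher adverse events a Fisher p-value but no risk difference or confidence interval, so the plan has no figure for how large an excess on Lambda is ruled out

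*Combined protocol and SAP*

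**What the plan says.** Section 5 (Study Design) makes safety an aim alongside efficacy: the study is "to evaluate the efficacy and safety of one dose of peginterferon-lambda-1a administered by injection (Lambda"). The Synopsis lists treatment-emergent adverse events as a secondary outcome in each cohort.

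Section 13.2.2 says how they are analysed. First, "Analysis of AE data will primarily be descriptive based on MedDRA coding of events". Two quantities are then singled out: "The proportion of participants experiencing an SAE and the proportion experiencing a Grade 3 or higher". The text continues "AE will be compared between randomized arms using Fisher"'s exact test. The section gives no risk difference, confidence interval, margin, expected event rate or safety power.

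Section 13.2.1 treats efficacy differently. It asks for the cumulative incidence in each arm and the difference between arms, and adds: "Statistical inference will use a two-sided Type 1 error rate of 0.05 and 95% confidence intervals". That sentence belongs to the infection and clearance analyses and is not repeated for adverse events.

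**The concern.** The recipients have no symptoms at entry, and about two thirds are expected to be uninfected (around 110 of 164, Section 13.1). Section 11 lists hepatobiliary toxicity as an identified risk and several other organ-system effects as potential risks. For a preventive injection in such people, the useful safety question is how large an excess of serious or severe events the trial can exclude.

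A p-value does not answer that. When events are few, it is usually above 0.05 whether the true excess is nil or substantial, and the two cases look alike. An interval separates what the data exclude from what they leave open. As written, efficacy gets a difference with an interval and safety gets a p-value.

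**Working it through.** **Inputs from the documents.** Section 13.1: "The planned sample size for the trial is 164 participants enrolled and randomized in a 1:1 ratio", so 164 / 2 = 82 per arm. The expected cohorts are about 110 (55 per arm) and about 54 (27 per arm). Section 13.2.1: two-sided 0.05, and "Analyses will include all randomized participants". Section 13.2.2: Fisher's exact test between randomized arms. **Assumption:** the adverse event rates, because the documents give none.

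**Step 1: check the method on the plan's own figures.** Power of the two-sided Fisher test is the sum, over all tables (i, j) with p ≤ 0.05, of Bin(i; n, p1) × Bin(j; n, p2). For infection on Lambda of 5%:

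| Placebo infection | n per arm | Computed | Section 13.1 |
|---|---|---|---|
| 25% | 55 | 80.1% | 80.1% |
| 40% | 55 | 99.6% | 99.6% |
| 25% | 27 | 36.1% | 36.1% |
| 40% | 27 | 84.0% | 84.0% |

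All four cells reproduce, so the same function is used below.

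**Step 2: what the p-value leaves unsaid (no assumed rate needed).** When one arm has no events, the two-sided Fisher p with equal arms is 2 × C(82, x) / C(164, x).

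- x = 5: p = 0.059.
- x = 6: p = 0.028. Six against none is therefore the smallest significant result. It is also six at 55 and at 27 per arm.

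The Newcombe interval for d = p1 − p2 uses the Wilson limits (l, u) of each arm:

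lower = d − √[(p1 − l1)² + (u2 − p2)²]; upper = d + √[(u1 − p1)² + (p2 − l2)²]

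*5 vs 0 of 82.* p1 = 6.10%, Wilson 2.63% to 13.49%; p2 = 0, Wilson 0 to 4.48%; d = 6.10 points.

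- Lower: 6.10 − √(3.47² + 4.48²) = 0.4.
- Upper: 6.10 + √(7.39² + 0²) = 13.5.

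*3 vs 1 of 82.* p1 = 3.66%, Wilson 1.25% to 10.21%; p2 = 1.22%, Wilson 0.22% to 6.59%; d = 2.44 points; Fisher p = 0.62.

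- Lower: 2.44 − √(2.41² + 5.37²) = −3.4.
- Upper: 2.44 + √(6.55² + 1.00²) = 9.1.

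*0 vs 0 of 82.* The upper limit is the Wilson limit, 3.84 / (82 + 3.84) = 4.5 points.

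**Step 3: chance of a non-significant result at 82 per arm, under assumed rates.**

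| Placebo vs Lambda (assumed) | Power | Missed |
|---|---|---|
| 1% vs 3% | 1.7% | 98% |
| 2% vs 6% | 11.6% | 88% |
| 5% vs 10% | 14.8% | 85% |
| 2% vs 10% | 45.9% | 54% |
| 5% vs 15% | 49.5% | 50% |
| 5% vs 20% | 80.5% | 19.5% |
| 5% vs 25% | 95.0% | 5% |

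By cohort the test is weaker: 5% vs 15% is missed 72% of the time at 55 per arm (power 28.5%) and 93% at 27 per arm (power 7.0%).

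**The case against.** The strongest reply is that the plan draws no conclusion from a non-significant test. A reader might infer that p > 0.05 will be presented as showing safety, but no section says so, and adverse event analysis is stated to be mainly descriptive. That stands: this is a gap in what is estimated and reported, not a false claim in the plan.

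A reader might also infer from the low-power scenarios that the test misses relevant harm at least half the time. The documents do not support that. They give no adverse event rates and define no relevant excess, and a large excess would usually be found (5% vs 20% is missed 19.5% of the time). The miss probability depends on the assumed rates.

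Nor is Fisher's test the only comparison bearing on tolerability. Section 8.4 gives FLU-PRO a role in picking up symptoms related to Lambda, and Section 13.2.2 gives it a Kruskal-Wallis test. Section 14.1 adds twice-monthly adverse event review and a DSMB review at 50%. These stand too, but a symptom scale does not compare serious or Grade 3 or higher events, and oversight during the trial does not specify an estimate for the final report.

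It can also be said that any reader could compute an interval from the reported proportions, and that low power for rare events is unavoidable in a trial sized on efficacy. Both are true. Neither is a reason to leave out the one figure that shows the imprecision.

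**Conclusion.** The point holds as a cheap improvement that should be made. Fisher's test is the only between-arm inference planned for adverse events, and it comes without an effect estimate or interval. The case rests mainly on Step 2, which needs no assumed event rate: at 82 per arm, results of 5 vs 0 and 3 vs 1 are both non-significant, yet leave excesses of up to 13.5 and 9.1 points open. The miss probabilities of about 98% to 5% illustrate the range under assumed rates and are not properties of the plan.

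The calculations assume 82 evaluable participants per arm with both cohorts pooled. Section 13.2.2 compares randomized arms while the Synopsis lists these outcomes by cohort, so the denominator needs stating. They also treat participants as independent, although Section 13.1 expects about two per household. Both Fisher's test and the Newcombe interval ignore that correlation.

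**What to change.** In Section 13.2.2, for any SAE and for any Grade 3 or higher adverse event:

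- Report counts and proportions by arm, and the Lambda minus placebo risk difference with a 95% Newcombe or exact interval. Do this over all dosed participants (about 82 per arm) and by cohort. Choose one interval method in advance.
- State that the safety conclusion is read from the upper limit, as the largest excess not excluded.
- Keep Fisher's p as supplementary, and state that p > 0.05 is not evidence of safety. Say that the interval governs where the two disagree, as they do at 5 vs 0, where the interval excludes zero but p = 0.059.
- Note that both the interval and Fisher's test ignore household correlation.

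The cost is a few sentences and one table column, with no new data or participants. The safety statement becomes visibly less reassuring: even with no events in either arm, the upper limit is about 4.5 points.

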13.2.3 Sensitivity analysis for missing data

We expect very low missingness of data in our results. We will explore the demographic and clinical characteristics comparing persons with full and incomplete follow-up, and try to define the mechanism of missingness with the input of study staff about clinical operations. This experiential input is necessary, because there is no data-driven mechanism to decide on non-ignorability of missing data. For Missing Completely At Random (MCAR) or Missing At Random (MAR) data mechanisms, as sensitivity analysis, we will use multiple imputation methods to test the robustness of our results.

14. Safety Oversight

14.1 Monitoring Plan

All AE and SAE will be reviewed by the protocol team twice monthly, or more if needed.

The Principal Investigator will be responsible for safety oversight of the clinical study.

A data safety monitoring board (DSMB), composed of independent experts without conflict of interests will be established. The Board will review the study before initiation and after 50% of planned enrolled participants have reached the primary endpoint. The Board will review study data to evaluate the safety, efficacy, study progress, and conduct of the study.

14.2 Study monitoring

As per ICH-GCP 5.18 and FDA 21 CFR 312.50, clinical protocols are required to be adequately

monitored by the study Sponsor/Investigator. Monitors will verify that:

- There is documentation of the informed consent process and signed informed consent documents for each participant.
- There is compliance with recording requirements for data points
- All SAEs are reported as required
- Individual participants' study records and source documents align
- Investigators are in compliance with the protocol.
- Regulatory requirements as per Office for Human Research Protections-OHRP, FDA, and applicable guidelines (ICH-GCP) are being followed.

14.3 Withdrawal criteria

Participants will be withdrawn from the study if they withdraw consent or if the study is cancelled.

14.4 Study stopping rules

We will pause enrollment after 50% of participants have reached study end point and wait until the DSMB has completed their planned review prior to resuming enrollment

We will use O'Brien and Fleming limits as the stopping rule based on efficacy (threshold p-values of 0.0054 at mid-planned sample and 0.0492 for the final analysis). For the futility stopping rule, we will use a conditional power of < 10% at the time of mid-sample accrual, assuming that the remaining sample will have the same treatment success as the sample accrued so far.

15. Protection of Human Subjects

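### The Section 14.4 efficacy thresholds (0.0054, 0.0492) are O'Brien-Fleming in shape but slightly too generous: with non-binding futility they spend 0.0513, not 0.05

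*Combined protocol and SAP*

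**What the plan says.** - **Section 14.4, boundary:** "We will use O'Brien and Fleming limits as the stopping rule based on efficacy", with "threshold p-values of 0.0054 at mid-planned sample and 0.0492 for the final analysis". No spending function is named.
- **Section 14.4, futility:** "we will use a conditional power of < 10% at the time of mid-sample accrual", projected on the treatment success seen so far. The text does not say whether this rule is binding.
- **Section 13.1, error rate:** "a two-sided Type I error rate (α) of 0.05".
- **Section 13.2.1, error rate:** "Statistical inference will use a two-sided Type 1 error rate of 0.05 and 95% confidence intervals". It does not refer to the final level in Section 14.4.
- **Section 14.1, timing:** the board reviews the data "after 50% of planned enrolled participants have reached the primary endpoint".
- **Section 13.1, cohorts:** it plans 164 enrolled and expects that "approximately 32.5% of participants who are enrolled have evidence of SARS-CoV-2 at study entry", leaving about 110 in Group A. Section 5 makes Group A the primary study population.

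**The concern.** A pair of O'Brien-Fleming limits for one interim look is fully determined by the overall error rate and the timing of the look. The printed pair does not match the stated 0.05 at one half.

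The consequence is a final threshold that is slightly too lenient. A final p-value between 0.0480 and 0.0492 would be declared significant under Section 14.4, but not under the O'Brien-Fleming limits that hold 0.05.

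Two gaps in wording go with this:

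1. Section 13.2.1 does not say whether 0.05 is the overall rate or the level of the final test. The overall rate is the natural reading, but the text does not settle it. A 95% interval also does not match a final level below 0.05.
2. The look is triggered by enrolment across both cohorts, while the efficacy question is in Group A. Fixed p-values hold 0.05 only at the information fraction for which they were solved.

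**Working it through.** **Inputs.** Thresholds 0.0054 and 0.0492 (14.4); two-sided 0.05 (13.1, 13.2.1); one look at information fraction t = 0.5 (14.1, 14.4); 164 enrolled, 32.5% positive at entry, 110 in Group A (13.1). Assumptions: large-sample normal statistics with correlation √t between looks, and futility non-binding unless stated.

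**Step 1: convert the printed p-values.** z = Φ⁻¹(1 − p/2) gives z₁ = 2.782 and z₂ = 1.967. The ratio is 1.4145, against √2 = 1.4142. The implied constant is 2.782/√2 = 1.967.

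**Step 2: total error of the printed pair.** Total α = P(|Z₁| ≥ z₁) + P(|Z₁| < z₁ and |Z₂| ≥ z₂). By numerical integration at t = 0.5:

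0.0054 + 0.0459 = 0.0513.

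A simulation of 20 million trials also gives 0.0513. Moving both p-values within their rounding gives 0.0512 to 0.0514.

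**Step 3: solve for the constant that holds 0.05.** With z₁ = C√2 and z₂ = C, total α = 0.05 at C = 1.9774. Then z = 2.797 and 1.977, so p = 0.0052 and 0.0480.

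| Interim / final level | Total two-sided α at t = 0.5 |
|---|---|
| 0.0054 / 0.0492 (as printed) | 0.0513 |
| 0.0052 / 0.0480 | 0.0500 |
| 0.0054 / 0.0479 | 0.0500 |
| 0.0054 / 0.05 (if 13.2.1 were read as the final level) | 0.0521 |

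**Step 4: look for another source of the printed pair.** The two common O'Brien-Fleming-type spending functions give 0.0031/0.0490 and 0.0056/0.0478 at t = 0.5; neither matches. The printed pair reaches 0.0500 only near t = 0.7, which is not mid-sample.

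**Step 5: timing in Group A.** Half of 164 is 82. The expected Group A count is 82 × 0.675 = 55.4, with SD √(82 × 0.675 × 0.325) = 4.2. Against a fixed 110, ±2 SD gives a fraction of 0.43 to 0.58. Over that range the printed pair spends 0.0518 to 0.0508. The timing is right on average, and the excess persists throughout.

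**Step 6: effect of futility.** Under the current trend, conditional power is 1 − Φ[(z₂ − z/√t)/√(1 − t)]. It equals 10% at interim z = 0.75. Error in the direction of benefit is 0.0256 if the rule may be overridden and 0.0229 if it is always obeyed.

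**Step 7: power cost.** Take the drift that gives 80.0% power with the printed pair. The same drift gives 79.7% with 0.0052/0.0480. The sample-size ratio that restores 80% is 1.0076, and 110 × 0.0076 = 0.84, fewer than one participant.

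**The case against.** The normal-theory arithmetic is not in dispute. The case against rests on four points.

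- **Futility.** The futility rule is worded as firmly as the efficacy limits. If it is always obeyed, total two-sided error is below 0.05: 0.0459 if applied symmetrically, 0.0256 if applied in one direction. This stands as a condition on the finding. However, the plan does not declare the rule binding or say that the efficacy limits depend on it.
- **The window at stake.** A spending function at t = 0.5 holds 0.05 with a final level of 0.0490, so against that boundary only 0.0490 to 0.0492 is affected at the final analysis. This is correct. The wider window, from 0.0480, belongs to the classical limits that Section 14.4 names.
- **Discreteness.** Exact enumeration with 55 independent participants per arm and no futility stop shows that the choice of test matters more than this edit. A logistic Wald test has error 0.0444 at a 25% infection rate and about 0.048 at 32.5%, under either pair. A pooled score test has about 0.052 to 0.053 at those rates under the printed pair, and the corrected pair lowers that by at most about 0.0005. This limits the practical effect. It does not make the printed limits correct, since such limits are defined by the normal approximation. The enumeration also omits the household random effect in the planned model.
- **Range of timing.** If enrolment runs to 164 and the final Group A count also varies, the fraction has SD 0.027 and a 95% range of 0.446 to 0.554, over which the pair spends 0.0517 to 0.0509. The wider range applies to a fixed Group A target of 110, which is how the synopsis describes the sample. The conclusion is the same either way.

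**Conclusion.** The concern holds and is minor. The printed pair has the O'Brien-Fleming shape with constant 1.967 where 1.977 is needed, and it spends 0.0513 instead of 0.05, an excess of 0.0013. This rests on the normal approximation, one look at half the information, and futility that may be overridden. Few possible results fall in the affected window, but this is a pre-specified rule for claiming efficacy and for early stopping, so it should match the stated error rate. The unclear role of 0.05 in Section 13.2.1, the pooled trigger for the look and the unstated status of futility are missing details; the finding does not depend on them.

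**What to change.** - **Section 14.4:** replace the thresholds with 0.0052 and 0.0480, or keep 0.0054 and set the final level to 0.0479. Alternatively, name an O'Brien-Fleming-type spending function and apply it at the actual Group A information fraction. Interim/final levels would be 0.0013/0.0496 at 0.43, 0.0031/0.0490 at 0.50 and 0.0065/0.0479 at 0.58.
- **Section 14.4:** state whether the futility rule is binding.
- **Section 13.2.1:** state that 0.05 is the overall two-sided error rate and that the final test uses the Section 14.4 level with the matching interval (about 95.2% for 0.0480).
- **Sections 14.1 and 14.4:** define the look by Group A participants with the primary outcome (55 of 110).

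The cost is two numbers and a few sentences, with no added participants. The final threshold becomes slightly stricter, and power falls from 80.0% to 79.7% by the normal approximation. That figure was not simulated under the planned mixed logistic model.
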